4. Have not received a specific vaccine against COVID-19 or, if vaccinated against SARS-CoV-2, have received the complete immunization schedule only with vaccines approved by ANVISA and implemented by the National Immunization Program, (including the second dose) within a minimum of 15 days prior to the date of inclusion in the study
5. If the participant have not received a specific vaccine against COVID-19 approved by ANVISA, be aware and agree to be able to receive them only 15 days after the intervention proposed in this study

Exclusion criteria:

1. Professionals with a history of sars-cov-2 confirmed infection through RT-PCR or who have already presented clinical and molecular diagnosis of COVID-19 prior to the study

2. Individuals who have not undergone confirmatory tests for COVID-19
3. Breastfeeding
4. Individuals who report having primary or acquired immunodeficiency
5. Individuals who report being affected by malignant neoplasms
6. Patients reporting treatment with high-dose corticosteroids (equivalent to the prednisone dose of 20 mg/day or more) for more than two weeks
7. Patients who report being on other immunosuppressive therapies (antineoplastic chemotherapy, radiotherapy, among others)
8. Individuals who report being diagnosed with autoimmune diseases
9. Dermatological conditions at the vaccine site or generalized
10. Individuals who report being treated for active tuberculosis
11. Individuals who report a history of previous treated tuberculosis
12. Individuals with febrile symptoms (body temperature $\geq 37.5^{\circ}\text{C}$ in the last 48h)
13. Participation in other clinical prevention trials for COVID-19 (vaccines already approved by ANVISA for use by the National Immunization Program are not included in this item)
14. Report of vaccination with live microorganism administered in the month prior to randomization
15. Require that, if another vaccination with live microorganism is required, it is administered in the month following randomisation (If the other live vaccine can be administered on the same day, this exclusion criterion does not apply)
16. Known anaphylactic reaction to any ingredient in bcg vaccine
17. Adverse reaction prior to BCG vaccine [significant local reaction (abscess) or suppurative lymphadenitis]
18. BCG vaccine administered in the last year

Intervention Plan:

Intervention:

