Health professionals from other institutions besides those participating in the study may participate in the research. In this case, they will contact the participating centers, through telephone contact or email, informing their interest. All follow-up of these participants will be carried out by the center in which the subject was recruited.

The first evaluation (*Screening* or recruitment) of the study can be initiated in person or through telephone contact, email or electronic media. If the eligibility criteria are met, the individual will be invited to attend the study center for the signing of the Informed Consent and collection of exams that will confirm his or her eligibility or not.

Over four other face-to-face visits [M0 or inclusion, M1 (10 days after the intervention), M3 (90 days after the intervention) and M6 (180 days after the intervention)] the *status* of Coronavirus infection will be monitored by real-time PCR, in the case of symptomatic, and coronavirus serology every 3 months after vaccination with BCG or placebo (chart below). The tests will be performed with the purpose of having the diagnosis of the infection either through the real-time polymerase chain reaction (RT-PCR) technique and/or through the qualitative identification of IgM+IgA and/or IgG antibodies in the detection of infections that occurred asymptotically and that may have been attenuated by the intervention with the BCG vaccine. For individuals receiving specific immunization against SARS CoV 2, serology will not be used for diagnosis of asymptomatic infection.

At the time of recruitment hiv serology and BHCG dosage will also be collected for *women with status* in order to meet the eligibility criteria. The time between the examinations collected in the recruitment and the effective inclusion in the study should be up to 10 calendar days. If the return occurs between the third and tenth day, and the

participant presents symptoms compatible with COVID-19 upon return, the participant should recollect the RT-PCR.

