In addition to face-to-face visits, participants will receive a telephone contact or a text message by phone via SMS or receive email, the *latter two with a link* for the participant to access and answer the questionnaire about signs and symptoms of COVID as well as sending a photo with the aspect of the injection site. This will occur weekly until M3, and then monthly seeking information on fever and/or respiratory symptoms and the site of vaccine application. The participant will be asked to send a photo of the vaccine application location in each of these contacts. If the participant signals any respiratory manifestation or fever, they will be instructed to seek the Worker Health Divisions of their respective work units or the private or public health services, according to their availability, for the nasoarcheal swab to perform RT-PCR for coronavirus, as well as for medical care directed to the condition. In case of adverse events to the vaccine or

placebo, patients will be evaluated in person at the study centers where they were recruited.

If any participant presents the diagnosis of OVID-19 they will be invited to attend the study for a face-to-face visit once they are asymptomatic and 14 days after the onset of symptoms. In this face-to-face visit, the participant will answer questions from a questionnaire about signs of symptoms of the disease and will be asked to present laboratory or radiological tests performed during COVID-19 infection.

Individuals who show interest in participating in the research should not have been previously vaccinated with any specific vaccine against COVID-19 or if vaccinated, only those immunized with both doses of vaccines, and the second dose should be applied within a minimum of 15 days.

Participants already included and submitted to the intervention, must wait up to 15 days after the intervention with BCG/Placebo to receive specific vaccines against COVID-19 already approved by ANVISA for use by the National Immunization Program, according to the guidelines of the Brazilian Ministry of Health.

In the case of recruited individuals who are eligible for inclusion and intervention, but who give up receiving the investigational product of the study, they should withdraw consent to participate in the ProBCG study.

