BCG vaccine:

The application of bcg vaccine as well as its storage and the materials used for application will follow the standards of the Manual of Standards and Procedures for Vaccination of the Ministry of Health (Brazil, 2014). As standardized in this Manual, the

vaccine will be applied intradermally to the lower insertion of the deltoid muscle of the right arm, except contraindications or impossibilities. Other details are described in the standard operating manual (MOP) of the study. After the intervention, participants will be under observation for 20 minutes in the study center waiting room and will be released after the period as long as they do not present adverse events.

Placebo:

A 0.1 ml of 0.9% NaCl saline solution applied intradermally in the lower insertion of the deltoid muscle of the right arm will be used as placebo, except contraindications or impossibilities. Other details are described in the standard operating manual (MOP) of the study. After the intervention, participants will be under observation for 20 minutes in the study center waiting room and will be released after the period as long as they do not present adverse events.

Blinding:

The study participants as well as the researchers, coordinators, nurses, physicians and digitizers of the study will be blind to the allocation in the experimental or control groups.

Only nursing technicians who will apply the vaccine or placebo will be aware of which group the patient will be allocated to. This professional will not follow up on the clinical follow-up or outcome of the study participant.

If the participant has access to the COVID-19 vaccine before 15 days after vaccination with the study product, the "blinding" may be performed at the participant's written request, and if the product applied was placebo, the same may be vaccinated against COVID-19 before the 15 days established by the National Immunization Program. Other details are described in the standard operating manual (MOP) of the study.

Reaction to BCG vaccine and placebo:

The BCG vaccine known to generate a local inflammatory response that lasts about 12 weeks and will be monitored throughout the study. The reactions are described below and will not be considered as adverse events:

- From the first to the second week: reddish macula lasting from 5 mm to 15 mm in diameter.
- From the third to the fourth week: pustule that forms with the softening of the center of the lesion, followed by the appearance of crust.

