We will also use for the two outcomes the sequential design the groups are followed up until there is a group with clear benefits or that both groups do not present difference. This design is used when the results need to be known very quickly. If there is a large difference between the treatments, then this study will be performed in a shorter time when compared to the parallel trial. The main ethical advantage is that if one treatment shows a superiority over the other, the study can already be stopped. However, the

interim analyses will be previously planned, in such a way that the calculation of sample size allows the multiplicity of the tests. The meaning of p-values in sequential analyses also changes, because when using sequential analyses, more than one analysis is performed, and the typical definition of a p-value as data "at least as extreme" as observed needs to be reset. One solution is to sort the p-values of a series of sequential tests based on the downtime and at what time the test statistic was in a certain appearance, known as ordering.

3. Assess the BCG vaccine-mediated immune response in healthcare professionals

SARS-CoV2 infection is estimated to occur in approximately 20% of health professionals vaccinated by BCG (experimental group), in 30% of health professionals not vaccinated by BCG (placebo group) and not vaccinated for COVID-19 and in 15% in COVID-19 vaccinated without BCG vaccine. A reduction of 10% to 15% of the joint effect of bcg vaccine with Covid-19 vaccine is expected.

In this scenario, with the bearing of 376 health professionals in each arm, if we assume that the percentage of covid-19 vaccinated is 80% and equal in each arm, SARS-CoV2 infection is expected to be detected in 15 professionals vaccinated only with BCG, in 23 professionals not vaccinated with BCG and COVID-19 vaccine, 45 professionals vaccinated for COVID-19 without bcg vaccine and 38 professionals vaccinated for COVID-19 and BCG. For each subgroup (vaccinated and not vaccinated with BCG) it will be possible to identify the predictive biomarkers of infection by comparing infected professionals with those who were not infected with SARS-CoV2.

INTERIM ANALYSIS PLAN:

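### Only placebo recipients who ask to be unblinded may take a COVID-19 vaccine before day 15, two other passages make everyone wait, and no analysis rule covers those who ask

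*Combined protocol and SAP*

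**What the plan says.** Three places in the protocol govern COVID-19 vaccination shortly after the study dose.

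- Inclusion criteria, item 5: a participant not yet vaccinated against COVID-19 must "be aware and agree to be able to receive them only 15 days after the intervention proposed in this study". The arm is not mentioned.
- Study visits: participants already included and treated "must wait up to 15 days after the intervention with BCG/Placebo to receive specific vaccines against COVID-19". Both products are named and no exception is given.
- Blinding: participants and most staff "will be blind to the allocation in the experimental or control groups". The section then adds a condition, "If the participant has access to the COVID-19 vaccine before 15 days after vaccination with the study product", under which the participant may request unblinding in writing. In that case, "if the product applied was placebo, the same may be vaccinated against COVID-19 before the 15 days established by the National Immunization Program". The operating manual is said to hold further detail.

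On the role of the COVID-19 vaccine, Primary Outcome 3 expects infection in 30% of those with neither vaccine and "in 15% in COVID-19 vaccinated without BCG vaccine". Its expected counts hold "if we assume that the percentage of covid-19 vaccinated is 80% and equal in each arm". On detection, the Study visits section states: "For individuals receiving specific immunization against SARS CoV 2, serology will not be used for diagnosis of asymptomatic infection". The Statistical Analysis Plan names modified intention-to-treat and per-protocol analyses. It does not say how an unblinded or early-vaccinated participant enters either.

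**The concern.** A site cannot follow all three passages. If the Blinding section prevails, two participants offered a vaccine appointment on day 5 are handled differently because of their allocation: the placebo participant may accept and the BCG participant may not. Three things are then at stake.

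- **Co-intervention.** The timing of a vaccine that the plan treats as halving infection risk becomes a consequence of the randomised arm.
- **Blinding.** Everyone who asks learns the arm, BCG recipients included. The section on reactions to BCG and placebo justifies placebo on the ground that people who know they were vaccinated may relax their precautions. It claims matched behaviour for at least the first month, and the unblinding rule operates inside that month. Case detection relies partly on participants reporting symptoms and seeking a swab, and knowledge of the arm can affect both.
- **M1 samples.** M1 falls on days 5 to 15. In the visit table it is the only scheduled post-dose biomarker draw in participants without COVID-19, and it serves primary objective 3. A COVID-19 dose taken before M1 can change antibody and biomarker values, and under the rule that happens in the placebo arm only.

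Recruitment ran from October 2020 to December 2021 and spans the vaccine roll-out that began in January 2021, so requests were foreseeable.

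**Working it through.** **The plan's own figures.** The expected infections under Primary Outcome 3 reproduce with 376 per arm and 80% COVID-19 vaccine uptake in each arm:

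- BCG only: 376 × 0.20 × 0.20 = 15
- Neither vaccine: 376 × 0.20 × 0.30 = 23
- COVID-19 vaccine only: 376 × 0.80 × 0.15 = 45
- Both, with the 15% joint reduction: 376 × 0.80 × 0.15 × 0.85 = 38

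The 376 itself does not follow from 30% against 20% with 80% power and two-sided 5% error. That calculation gives 294 per arm, or 313 with continuity correction. This is not the issue here. It means that the baseline power at 376 is above 80%:

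Power = Φ{[√n·d − 1.96·√(2p̄(1−p̄))] / √(p₁(1−p₁) + p₂(1−p₂))}

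With n = 376, p₁ = 0.30, p₂ = 0.20 and d = 0.10, this is Φ{(1.939 − 1.200)/0.608} = 88.8%.

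**Effect of timing alone.** The inputs are 6-month risks of 30% without and 15% with the COVID-19 vaccine. Assumptions: constant hazards over 180 days, immediate protection, and BCG requesters vaccinated at day 15.

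- Daily hazard unvaccinated: −ln(0.70)/180 = 0.00198
- Daily hazard vaccinated: −ln(0.85)/180 = 0.00090
- Risk if vaccinated at day 0: 15.0%
- Risk if vaccinated at day 15: 1 − exp[−(15 × 0.00198 + 165 × 0.00090)] = 16.4%

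The gap is 1.4 points per requester. It lowers the placebo rate and so pulls the comparison towards no difference. The documents give no share of participants who ask, so f is assumed:

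| f | Shift in placebo rate | Planned 10-point difference becomes | Power at 376 per arm |
|---|---|---|---|
| 10% | 0.1 | 9.9 | 88.0% |
| 20% | 0.3 | 9.7 | 87.1% |
| 50% | 0.7 | 9.3 | 84.4% |

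The plan's own cell rates at 80% uptake imply a smaller difference. The placebo rate is 0.2 × 0.30 + 0.8 × 0.15 = 18.0%, and the BCG rate is 0.2 × 0.20 + 0.8 × (38/300.8) = 14.1%. Against those 3.9 points, the shifts at f = 10% and 20% leave 3.8 and 3.6.

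**Extreme bound.** Suppose BCG requesters never take a COVID-19 vaccine while placebo requesters fall from 30% to 15%. The shift is f × 15 points: 1.5 at f = 10% (difference 8.5, power 77.7%) and 3.0 at f = 20% (difference 7.0, power 62.0%). Nothing in the documents says that this would happen.

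**M1.** No arithmetic is needed. If the Blinding section is followed, participants vaccinated against COVID-19 between the study dose and day 15 are all in the placebo arm. Splitting the immune analysis by COVID-19 vaccine category does not solve this, because that group has no BCG counterpart.

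**The case against.** The strongest defence is that the exception is deliberate. The section on specific COVID-19 vaccines explains the interval by the lack of co-administration data, and saline is not a vaccine. On that view the defect is a missing cross-reference. The differing wording of the wait (only after 15 days, or up to 15 days) may be translation noise. This explains the exception but does not remove the conflict with criterion 5. It also supplies no analysis rule.

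Some of the plan helps. Participants who enter fully vaccinated against COVID-19 are unaffected. The objectives for co-vaccinated participants take the time to COVID-19 vaccination into account. However, those objectives concern a subgroup, and the timing itself depends on arm.

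Several stronger readings are tempting, and the documents do not support them.

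- *The equal-uptake assumption is broken by rule.* That assumption concerns the percentage vaccinated. The rule shifts timing by up to 15 days, and BCG recipients may be vaccinated afterwards.
- *Infection detection becomes unequal because serology is dropped.* A BCG requester vaccinated from day 15 also loses serological detection before M3, so the rule alone creates no gap at M3 or M6.
- *Days 0 to 14 are half of a 30-day risk window, filled with vaccine fever in one arm.* The Statistical Analysis Plan gives 30 days as a time of analysis, not clearly as a per-person window. The fever rate above 30% is for Covishield; for Coronavac fever is listed at 10% or less. BCG requesters can have the same reactions from day 15. Fever alone is not a primary case in a COVID-19-vaccinated person.
- *Under-reporting by people who know they had BCG gives a quantifiable spurious benefit.* No reporting rate is given. The pustule at weeks 3 to 4 and the later ulcer and scar would reveal the arm to many BCG recipients anyway, so the rule adds mainly the first weeks.
- *M1 is the only immune sample after the dose.* Antibodies are also measured at M3 and M6, and the Immunoassays section lists M3 and M12 for biomarkers, contrary to the visit table.

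**Conclusion.** The contradiction is plain in the text: the Blinding section permits for one arm what criterion 5 and the Study visits section withhold from both. Its direct effect on the 6-month infection comparison is small, at most about 1.4 points per requester and 0.1 to 0.3 points at an assumed 10% to 20% requesting. The 1.4 rests on constant hazards and immediate protection. The latter probably overstates it, since the plan cites Covishield efficacy from 22 days after the first dose. A material bias would require later COVID-19 vaccine uptake to differ by arm as well.

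The firmer consequences are open-label follow-up for requesters in the month for which placebo was justified, and M1 contamination confined to one arm. Neither can be sized from the documents. Unblinding is certain only for the participant; whether assessors also learn the arm may be settled in the operating manual, which is not available here. The change is worth making, but this does not by itself undermine the primary infection result.

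**What to change.** 1. The sponsor should reconcile inclusion criterion 5, the Study visits section and the Blinding section, including the two wordings of the wait. No view is taken here on the interval or on whether the exception should stand.
2. Log each request before disclosure, then the unblinding date and the COVID-19 vaccination date. The nursing technician, who already knows the allocation, should disclose it to the participant only, so that assessors stay blind.
3. Keep all requesters in their randomised arm in the primary analysis. Prespecify a sensitivity analysis that excludes all requesters in both arms, and state how they enter the modified intention-to-treat and per-protocol sets.
4. For the M1 immune comparison, exclude all requesters in both arms. Define the exclusion by the request, which precedes disclosure, and not by receipt of a COVID-19 dose, which under the current rule would remove placebo participants only. Report requests by arm as a check, because a skin reaction in the first two weeks could prompt some of them.

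The cost is protocol wording, two or three log fields, one extra analysis and a slightly smaller M1 set.

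Deferring randomisation for people with an imminent vaccine appointment is optional and a trade-off. Criterion 4 requires the complete schedule plus at least 15 days. With the 8 to 12 weeks between doses that the plan cites for Covishield, that means about 10 to 14 weeks from the first dose (56 + 15 = 71 days to 84 + 15 = 99 days), against recruitment ending on 31 December 2021.
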